#### 5.1.5 Rescue Therapy Guidelines

Rescue therapy guidelines are provided to optimize standardization of the use of rescue therapy by investigators and to ensure safety of the individual study subjects. Details of the rescue therapy will be recorded in the eCRF.

##### 1. *RBC Transfusion* (for all subjects)

RBC transfusion is allowed if rapid correction of anemia is required to stabilize the patient's condition or the investigator is of the opinion that the RBC transfusion is a medical necessity. Study treatment may continue during or after transfusion administration. Hb needs to be measured pre- and posttransfusion (HemoCue®).

##### 2. *ESA* (only for subjects treated with roxadustat)

One course of rescue ESA is allowed. If the investigator considers administration of ESA as a medical necessity, 1 course of rescue ESA may be initiated if the following criteria are met:

- the Hb level has not responded adequately despite 2 or more roxadustat dose increases in the previous 8 weeks, or the roxadustat dose has reached the maximum dose limit, and
- the subject's Hb level is < 9.0 g/dL (HemoCue®) as confirmed at 2 consecutive study visits, and
- reducing the risk of alloimmunization in transplant eligible subjects and/or reduction of other RBC transfusion-related risks is a goal.

Prior to the initiation of rescue ESA (epoetin alfa for subjects treated with any epoetin prior to randomization; and darbepoetin alfa for subjects treated with darbepoetin alfa prior to randomization), the subject's Hb response, as well as factors influencing the Hb response, such as iron status, inflammatory status, hemolysis, blood loss or other potential reasons for Hb decrease should be considered and, where applicable, addressed by the investigator. Prior to initiating ESA rescue therapy, iron deficiency should be corrected (i.e. 100 ng/mL [220 pmol/L] ferritin and 20% TSAT).

The subject may continue on study, however, the subject is not allowed to be administered both rescue ESA and roxadustat during the same time period. The course of rescue ESA (i.e. the amount that may be administered) will be limited by duration of therapy and effect on Hb, including that 1 course of treatment with rescue ESA will not exceed 4 weeks in duration, and that ESA rescue will be stopped as soon as Hb  $\geq$ 9.0 g/dL as measured by HemoCue. Treatment with roxadustat may be resumed as soon as possible after the following intervals:

- At least 2 days after stop of epoetin alfa
- At least 1 week after stop of darbepoetin alfa

If a subject requires a second course of rescue with ESA, the subject must be discontinued from study treatment. The subject will complete the EOT visits (EOT visit and EOT + 2 weeks visit) and EOS visit, and will continue to be followed up at a 6-monthly frequency for vital status, SAEs and cardiovascular and thromboembolic AEs until their projected date of completion or until consent withdrawn.

**Doses:** The doses of rescue therapies are at investigator's discretion.

## **Emergency procedure**

### ***Therapeutic Phlebotomy***

If there are clinical concerns for a subject's high Hb levels, the investigator may decide to perform a therapeutic phlebotomy instead of, or in addition to, a study treatment dose hold. This should be documented in the eCRF and source documentation, and discussed with the study medical monitor.

#### **5.1.6 Restrictions During the Study**

- Subjects are not permitted to consume more than 3 alcohol-containing drinks per day during the treatment or follow-up periods.
- If heterosexually active, female subjects of childbearing potential will be required to use a highly effective form of birth control. If required by local law, 2 highly effective methods of birth control must be used, 1 of which must be a barrier method.
- Heterosexually active male subjects with female partners of childbearing potential should also use a highly effective form of birth control. If required by local law, 2 highly effective methods of birth control must be used, 1 of which must be a barrier method.

- Contraception must be practiced from start of screening until 28 days (female subjects), and until 12 weeks (male subjects with female partners of childbearing potential) after the last dose of study treatment. If a subject discontinues prematurely, contraception must be practiced for 12 weeks (male subjects) and 28 days (female subjects) following final administration of study treatment.
- Pregnancy, spontaneous or therapeutic abortion, or events related to pregnancy must be reported (see Section 5.5.8).

## 5.2 Demographics and Baseline Characteristics

### 5.2.1 Demographics

Demographic data recorded during screening, including date of birth (depending on local regulations, if full date of birth cannot be recorded only year of birth will be recorded), sex and race will be recorded in the eCRF.

### 5.2.2 Medical History

A detailed medical history, including detailed cardiovascular history and family cardiovascular history, will be obtained at screening. All relevant past and present conditions as well as previous and current tobacco use will be recorded in the subject's eCRF. Relevant conditions include conditions that have been treated with medication within 4 months prior to randomization. Additionally, family history of cardiovascular diseases in first degree relatives (occurring before the age of 60) will be obtained.

### 5.2.3 Renal Ultrasound

A renal ultrasound examination can be performed at any time during the screening period. This can be replaced by a pre-existing examination (or other renal imaging modality such as CT or MRI scan if it was conducted within 12 weeks prior to randomization and it conclusively excludes the presence of renal cell carcinoma). Examination results must be available prior to randomization (see exclusion criterion 15). The date and assessment for the absence, presence or suspicion of renal cell carcinoma will be collected in the eCRF.

### 5.2.4 Diagnosis of the Target Disease, Severity, and Duration of Disease

A detailed anemia and CKD history for each subject will be obtained at screening and recorded in the eCRF. This includes date of diagnosis and symptoms of anemia, the date of diagnosis of CKD, etiology, vascular access history, date of initiation of current and first dialysis and mode of current and first dialysis. Also the nondrug therapy history and medication history for anemia (last 12 months) and the nondrug therapy history for CKD (last 4 months) prior to randomization will be obtained.

Anemia will be measured by repeated Hb measurements (central laboratory assessment) during screening; the mean of the 3 most recent Hb values during the screening period, obtained at least 4 days apart, must be  $\geq 9.5$  g/dL and  $\leq 12.0$  g/dL, with an absolute difference of  $\leq 1.3$  g/dL between the highest and the lowest values. The last Hb value must be within 10 days prior to randomization.

Exclusion of other causes of anemia should be based on an integrated assessment of clinical and laboratory signs and symptoms as well as medical history.

### **5.2.5 Further Laboratory Testing Prior to Randomization**

Other laboratory tests mandatory prior to randomization of a subject, for eligibility or baseline purposes, include enzyme-linked immunosorbent assay for human immunodeficiency virus, Hepatitis B surface antigen and anti-hepatitis C antibody and serum pregnancy test for women of childbearing potential only, serum chemistry and serum lipid panel.

For more details on the laboratory tests please refer to Section [5.4.3](#)

## **5.3 Efficacy Assessment**

### **5.3.1 Primary Efficacy Assessment**

The assessment of the efficacy of the study treatments will be based primarily upon Hb as assessed by central laboratory from IV blood sampling.

For the exact timing of Hb assessments refer to the Schedule of Assessments [Table 1](#).

The use of concomitant medication (as recorded in the eCRF) will be taken into account for the evaluation of the primary efficacy assessment.

### **5.3.2 Secondary Efficacy Assessments**

#### **5.3.2.1 Blood Pressure**

Blood pressure will be assessed as per schedule of assessment, SBP and DBP will be measured and MAP will be calculated. Blood pressure will be measured before and after dialysis in HD patients. In PD patients, blood pressure will only be measured at 1 time point on the examination day, irrespective of current dialysis cycle. For details on the measurement of blood pressure refer to Section [5.4.1.1](#)

#### **5.3.2.2 Serum Lipid Panel**

Blood sampling for serum lipids should be done in a fasting condition, wherever possible. The following parameters will be assessed: total cholesterol, LDL-cholesterol, HDL-cholesterol, triglycerides, apolipoproteins A1 and B.

### **5.3.3 Additional Assessments**

#### **5.3.3.1 Health Related Quality of Life Questionnaires**

All study subjects will be required to complete the following 4 QoL questionnaires: SF-36, FACT-An, EQ-5D 5L and PGIC (see Appendices). The timing of the questionnaires is indicated in the Schedule of Assessments [Table 1](#).

In HD subjects the QoL questionnaires are to be completed by the subject prior to or at the latest at the start of the dialysis session. It is important that the investigator does not discuss the status of the subject prior to completion of the questionnaires.

In PD subjects, the QoL questionnaires are to be completed prior to any other study assessment.

### 5.3.3.1.1 Short Form-36 Health Survey (SF-36)

The SF-36 is a QoL instrument designed to assess generic health concepts relevant across age, disease, and treatment groups. It is aimed at both adults and adolescents aged 18 years and older. The SF-36 consists of 8 domains of health status: Physical functioning (10 items), Role-physical (4 items), Bodily pain (2 items), General health (5 items), Vitality (4 items), Social functioning (2 items), Role emotional (3 items) and Mental health (5 items). Two component scores, the Physical Component Summary and the Mental Component Summary can also be calculated. For both the SF-36 domain scores and summary scores, higher scores indicate better health status. The SF-36 has a recall period of the ‘past 4 weeks’.

### 5.3.3.1.2 Functional Assessment of Cancer Therapy –Anemia (FACT-An)

The Functional Assessment of Cancer Therapy- General (FACT-G) Version 4 contains 27 items that cover 4 dimensions of physical well-being (PWB)—7 items, functional (FWB)—7 items, social/family (SWB)—7 items each, and emotional (EWB)—6 items. A subscale of 13 fatigue specific items (the Fatigue Subscale) plus seven additional items related to anemia were developed for use in conjunction with the FACT-G [Cella , 1997]. The 13 fatigue items plus the 7 additional items related to anemia comprise the Anemia Subscale (AnS). Administration of the FACT-G plus the AnS is referred to as the FACT-An (Appendix 12.5). The FACT-An has a recall period of the ‘past seven days’. Respondents are asked to provide responses, (i.e. ‘Not at all’, ‘A little bit’, ‘Somewhat’, ‘Quite a bit’ and ‘Very much’), to a list of statements which are either positively or negatively phrased. For all FACT-An scales, a higher score indicates better QoL.

### 5.3.3.1.3 EuroQol Questionnaire – 5 Dimensions 5 Levels (EQ-5D-5L)

The EuroQol Questionnaire -5 Dimensions -5 Levels (EQ-5D-5L) is a self-reported questionnaire. The EQ-5D is being used as a measure of respondents' Health Related Quality of Life (HRQoL) and utility values. The EQ-5D consists of the EQ-5D descriptive system and the EQ visual analogue scale (VAS). The EQ-5D descriptive system comprises 5 dimensions of health: mobility, self-care, usual activities, pain/discomfort, and anxiety/depression. Each dimension has 5 levels: no problems, slight problems, moderate problems, severe problems, extreme problems. The VAS records the respondent's self-rated health status on a graduated (0–100) scale, where the endpoints are labeled ‘Best imaginable health state’ and ‘Worst imaginable health state’ with higher scores for higher HRQoL. EQ-5D health states, defined by the EQ-5D descriptive system, may be converted into a single summary index. The EQ-5D-5L is shown in Appendix 12.6

### 5.3.3.1.4 Patient Global Impression of Change Scale (PGIC)

The PGIC (Appendix 12.7) is a subject-rated instrument that measures change in subjects’ overall status on a 7-point scale ranging from 1 (very much improved) to 7 (very much worse), when compared to the start of the study treatment.

### 5.3.3.2 Hospitalizations

Details on hospitalizations will be collected at each study visit as indicated in the Schedule of Assessments. Reason, admission and discharge dates and type and reason for hospitalization

will be recorded in the eCRF. Details of hospitalizations will also be collected at poststudy follow-up visits in subjects who prematurely discontinued treatment (only if they have taken at least 1 dose of study drug), until the projected date of the EOS visit.

HD within the hospital is not considered to be a hospitalization, even when occurring overnight.

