In case that several Hb values are on the same day the average of these values will be used to represent the Hb of that day in the above formula. This calculation will provide the day that the change in Hb value occurs. The number of days that the Hb value has been in each category will be determined and the percentage calculated based on the length of time between the first and last Hb assessment during the evaluated period, i.e.:

Date of Last Hb assessment during the evaluated period – Date of first assessment during the evaluated period.

No imputation will be performed if no Hb value is available in relevant time windows.

In case a subject requires rescue therapy within 6 weeks prior to and during these 8-week evaluation periods, refer to Section 7.11.1 for imputation rules.

Potential Excessive Hematopoiesis (EH), regardless use of rescue therapy, based on Hb central laboratory

The presence of potential EH will be defined as:

- Hb increase by >2.0 g/dL between any 2 visits within 4 weeks of treatment

Time to first occurrence of potential EH regardless the use of rescue therapy during the treatment period will be defined in weeks as:

$$(\text{First event date} - \text{Analysis date of first dose} + 1) / 7$$

where ‘First event date’ is defined as first date of occurrence of the criterion met during the treatment period.

For a subject without potential EH, the time to censoring will be calculated (in weeks) as:

$(\text{Min}(\text{Date of last hemoglobin assessment during the Efficacy Emergent Period, End Date of the Efficacy Emergent Period}) - \text{Analysis date of first dose} + 1) / 7$

Refer to Section [7.11.6](#) for the definition of the Efficacy Emergent Period.

6.1.3.6 Occurrence (number) of hospitalizations, number of days of hospitalization per year and time to first hospitalization.

The occurrence and the number of non-HD hospitalizations per subject during the Efficacy Emergent Period will be calculated. HD days are not counted as hospitalizations, even when performed overnight.

The number of days of hospitalization per year treated will be calculated as:

$[\text{Sum of the durations of all non-HD hospitalizations in days (Date of discharge} - \text{Date of admission} + 1)] / (\text{duration of efficacy emergent period in days} / 365.25)$.

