In case of missing dates, the hospitalization duration will be imputed by the average duration per stay derived from the subjects with non-missing duration within the same treatment group. Duration of treatment exposure is defined in Section [6.5.4](#)

If the date of admission of a hospitalization record is the same as the date of discharge of the previous record, for example because two records are created to illustrate that the subject is moved from one hospital to another hospital or from a standard care to the intensive care unit (ICU), then the two records will be combined in one record.

Hospitalizations will also be described by reason for admission (admission for anemia or other reasons).

Time to first hospitalization in years will be defined in years as:

$(\text{First event date during the Efficacy Emergent Period} - \text{Analysis date of First dose intake} + 1) / 365.25$

With 'First event date' defined as 'Date of first Admission and 'Analysis Date of first dose intake' defined in Section [6.5.4](#)

For a subject without hospitalization, the time to censoring will be calculated as:

$(\text{Date of End of Efficacy Emergent Period} - \text{Analysis Date of first dose intake} + 1) / 365.25$

With date of End of Efficacy Emergent Period defined in Section [7.11.6](#)

6.1.3.7 Occurrence and time to first use of rescue therapy, occurrence and time to first use of RBC transfusions, number of RBC packs per subject, volume of RBC transfused per subject during the treatment period.

Rescue therapy is defined as RBC transfusion for all subjects and ESA (SC or IV) for roxadustat-treated subjects.

RBC transfusion is collected and coded into the ATC and WHO-DRL dictionaries. The following WHO-DRL codes will be classified as RBC transfusion: '01186901001'. ESA rescue treatment is recorded on the dosing CRF.

Only rescue medication that started during the study treatment and up to end of efficacy emergent period will be taken into account and considered as use of rescue medication.

For a subject with use of rescue therapy, the time to first use of rescue therapy will be calculated (in years) as:

$$(\text{First event date} - \text{Analysis Date of first dose intake} + 1) / 365.25$$

With 'First event date' defined as 'Date of first dose of rescue medication' during the Efficacy Emergent Period and 'Analysis date of first dose intake' defined in Section 6.5.4

For a subject without use of rescue therapy, the Time to censoring is calculated as:

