In addition, the randomization stratification strata from both sources (CRF and IRS) will be reported by treatment arm. Discrepancy between stratification from CRF and IRS will be summarized and the total number of patients with discrepancy overall and for each stratification factor will be provided.

Subjects who had a screen failure will be listed.

All other available data will also be listed.

All data collected during the Post-Study Follow up period will be listed by visit (i.e., type of contact, subject status and occurrence of overnight hospitalizations).

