7.4.3.5 Categorical analysis for Hb values

For the analyses below, results will be displayed by treatment arm and type of ESA treatment.

Proportion of Hb values:

The proportion of Hb values >=10 g/dL and within 10-12 g/dL is a quantitative variable in the 0 – 100 range for each subject. Descriptive statistics for this variable will be presented. This variable will be presented in weeks 28-36, in weeks 44-52 and in weeks 96 -104, on the FAS.

Percentage of time during the Efficacy Emergent Period:

Descriptive statistics for the percentage of time with Hb values falling in each interval (<10.0 g/dL, >=10 g/dL, within 10.0-12.0 g/dL, > 12.0 g/dL, > 13.0 g/dL and > 14.0 g/dL) between the first and last Hb assessment during the Efficacy Emergent Period will be presented.

The number and percentage of subjects, and the number of events, will be reported by for the following potential EH events of interest, based on Hb values from the central laboratory:

- Hb increase by >2.0 g/dL between any two visits within 4 weeks of treatment

Time to first occurrence of potential EH will also be analyzed similarly as in Section [7.4.2.7](#) (except that all data during the Efficacy Emergent Period will be taken into account for the analysis).

Subjects with at least one Hb value > 13 g/dL during the treatment period will be summarized.

7.4.3.6 Occurrence (number) of hospitalizations, number of days of hospitalization per year and time to first hospitalization during the study.

The number and percentage of subjects with hospitalization will be reported. Descriptive statistics and frequency tabulations by treatment arm and type of ESA treatment of the total duration of hospitalization (days), the average duration of each hospitalization (days), the number of hospitalizations, number of days of hospitalization per year and reason for hospitalization will also be reported.

Time to first hospitalization will also be analyzed similarly as in Section [7.4.2.7](#) (except that all data during the Efficacy Emergent Period will be taken into account for the analysis).

Superiority will be declared if the upper bound of the two-sided 95% confidence interval of the hazard ratio of the two treatment arms is below 1.

The analysis will be done on the FAS.

7.4.3.7 Occurrence and time to first use of rescue therapy, occurrence and time to first use of RBC transfusions, number of RBC packs per subject, volume of RBC transfused per subject.

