7.11.6 End of Efficacy Emergent Period

For all subjects, the end of Efficacy Emergent Period is defined as the treatment period up to the EOT Visit. Only exception for subjects who discontinued due to death, the last Hb assessment is taken as per convention the date of death is the EOT visit.

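### The hospitalization superiority statement rests only on follow-up to the end-of-treatment visit although later admissions are collected; if stopping depends on prognosis differently by arm, the hazard ratio is biased in an unknown direction

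*Protocol*

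**What the plan says.** **Collection.** Protocol 2.3.3.1 lists the number of hospitalizations and the days in hospital as additional secondary endpoints and sets no on-treatment limit. Section 5.3.3.2 extends collection beyond treatment: "Details of hospitalizations will also be collected at poststudy follow-up visits in subjects who prematurely discontinued treatment", if they took at least one dose, until the projected EOS date.

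**Analysis window.** SAP 6.1.3.6: "The occurrence and the number of non-HD hospitalizations per subject during the Efficacy Emergent Period will be calculated". For time to first admission, "For a subject without hospitalization, the time to censoring will be calculated as" the time from first dose to the end of that same period. SAP 7.11.6 closes the period: "the end of Efficacy Emergent Period is defined as the treatment period up to the EOT Visit". For subjects who discontinued because they died, the last Hb assessment closes it instead.

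**Test.** SAP 7.4.3.6: "Time to first hospitalization will also be analyzed similarly as in Section" 7.4.2.7, meaning a Cox model, here restricted to Efficacy Emergent Period data and run on the FAS. Superiority is declared if the upper limit of the two-sided 95% CI for the HR is below 1.

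**Later records.** SAP 7.2.1: "All data collected during the Post-Study Follow up period will be listed by visit", naming type of contact, "subject status and occurrence of overnight hospitalizations". SAP 7.5.1.2 also tabulates serious AEs from the post-study period. Neither is a comparison of hospitalization between arms.

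**Stopping rules.** Protocol 6.1 includes physician decision, in an open-label trial. One rule applies to roxadustat subjects only (also in Protocol 5.1.5): "If a subject requires a second course of rescue with ESA, the subject must be discontinued from study treatment".

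**The concern.** Censoring at EOT is harmless only if subjects who stop have the same future admission risk as comparable subjects who stay. If sicker subjects stop more readily in one arm, they leave that arm's risk set before being admitted, and that arm's observed hazard falls with no drug effect.

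The plan gives reasons to take this seriously. One mandatory stopping rule exists in one arm only, and physicians can stop open-label treatment at their discretion. The SAP also anticipates imbalance. Its revision history (version 2.0) cites an expected difference in treatment durations as one reason for adding time to first hospitalization, and SAP 7.5.1.4 refers to differing discontinuation rates when it motivates the AE incidence rates. A time-to-event analysis corrects for unequal duration only when the censoring is non-informative.

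Deaths add a smaller gap. Visits after week 36 are four weeks apart, so a final admission that begins after the last Hb assessment is not counted. The SAP already does better for mortality: 6.2.1.3 analyses deaths through post-study follow-up to Day 760.

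At stake is a nominal superiority statement on an outcome that readers notice, plus the loss of events that sites were asked to collect.

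**Working it through.** **Inputs.** The documents give no admission rate, discontinuation rate or power for hospitalization, so there is no plan figure to reproduce. From the documents: 1:1 allocation, 375 per arm, 52 to 104 weeks of treatment, success if the upper 95% limit is below 1 (one-sided 2.5%). Assumed: first-admission rate h = 0.7/year (0.4 in one run), stopping rate d as shown, and frailty z with a gamma distribution, mean 1 and variance θ = 0.5 to 2.

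**Mechanism.** Let the admission hazard be h·z and the stopping hazard d·z where stopping is linked to prognosis. Among subjects still at risk at time t, mean frailty is 1/(1 + θ(h + d)t). If stopping is unlinked, or follow-up continues after stopping, it is 1/(1 + θht). The apparent HR at time t is the ratio of these means. At t = 1 year with h = 0.7 and θ = 1:

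- linked in both arms, d = 0.3 vs 0.2: (1 + 0.9)/(1 + 1.0) = 0.95
- reversed, 0.2 vs 0.3: 2.0/1.9 = 1.05
- linked in roxadustat only, d = 0.3: (1 + 0.7)/(1 + 1.0) = 0.85
- unlinked in both arms, or equal and equally linked: 1.00
- follow-up continued after stopping: 1.7/1.7 = 1.00

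The bias starts at zero and grows with time, so the whole-trial HR lies nearer 1 than these one-year values.

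**Simulation, true HR = 1.** 370 or 375 per arm, 1 to 2 years of follow-up, 2000 to 3000 trials per scenario, unadjusted HR, no deaths or losses. The Monte Carlo standard error at 2.5% with 3000 trials is √(0.025 × 0.975/3000) = 0.3 points.

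| Stopping per year, roxadustat vs ESA | HR, EOT censoring | False superiority |
|---|---|---|
| Unlinked, 0.3 vs 0.15 (36% vs 20% stop) | 1.00 | 2.4% |
| Linked in both, 0.25 vs 0.2, θ 0.5–1 | 0.99 | 2.5–3.6% |
| Half the stopping hazard linked, 0.3 vs 0.2, θ 0.5–1 | 0.99–0.98 | 2.7–3.7% |
| Linked in both, 0.3 vs 0.2, θ 0.5–2 | 0.98–0.96 | 3.8–5.8% |
| Linked in both, 0.2 vs 0.3, θ 0.5–1 | 1.01–1.03 | 1.2–1.8% |
| Linked in both, 0.4 vs 0.2, θ 0.5–2 | 0.96–0.92 | 5.7–9.5% |
| Linked in roxadustat only, 0.2 vs 0.2, θ 1 (23% vs 26% stop) | 0.93 | 9.2% |
| Linked in roxadustat only, 0.3 vs 0.15, θ 1 (31% vs 20%) | 0.905 | 13.9% |
| Same, θ 0.5 (33% vs 20%) | 0.94 | 8.3% |
| Same, θ 1, admission rate 0.4 | 0.88 | 14.4% |

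Where the trials were also followed to the projected EOS, the HR was 1.00 and false superiority 2.2 to 2.5%.

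**Events lost.** From (380 − 336)/380 = 12% (unlinked, 0.3 vs 0.15) to (317 − 258)/317 = 19% (0.4 vs 0.2, θ = 2) of first admissions fall after treatment stop.

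**Different questions.** If admission risk doubles after stopping in both arms (one-sided linkage, 0.3 vs 0.15, θ = 1), EOT censoring still shows 0.905, while full follow-up shows 1.03 because more roxadustat subjects stop. The two analyses are not interchangeable.

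**The case against.** A fair defence has five parts.

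- **On-treatment follow-up is a legitimate, prespecified choice.** SAP 6.1 makes the Efficacy Emergent Period the default for efficacy time-to-event endpoints, and Protocol 7.4.3 leaves these analyses to the SAP. After EOT, anemia treatment is at the investigator's discretion, so roxadustat subjects may return to an ESA and later time dilutes a true effect. This stands. It supports keeping the analysis, not making it the only basis for a superiority statement.
- **The stakes are limited.** This is an additional secondary endpoint outside the nine-test sequence, and time to first hospitalization was added in the SAP. This stands, and it sets the priority.
- **The size is assumed.** No document links stopping to prognosis. The reasons for stopping also include transplant, consent withdrawal and noncompliance, and the roxadustat-only rule needs a second rescue course. The 9.5% figure needs doubled, fully linked discontinuation and θ = 2. The planned Cox model is stratified by region, CV history and previous ESA and adjusted for baseline Hb, which should absorb some shared prognosis. This stands.
- **The later data are not simply discarded.** Protocol 5.5.5 makes any post-study event leading to hospitalization reportable as an SAE, and SAP 7.5.1.2 tabulates post-study serious AEs. True, but without a hospitalization comparison.
- **Dated admissions may not exist.** Protocol 5.3.3.2 ties admission and discharge dates to study visits and promises only details afterwards. SAP 7.2.1 speaks of occurrence, and collection is six-monthly by phone or from clinic records. This stands and must be settled first.

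**Conclusion.** The gap is real: hospitalization details are collected to the projected EOS, no planned hospitalization analysis uses them, and a nominal superiority statement rests on the EOT-censored window alone. The harm is conditional. It needs stopping that depends on prognosis differently by arm, which is plausible here but not shown. Under the assumed rates, moderate imbalance gives an HR of about 0.96 to 0.99 and false superiority of about 3 to 6%. One-sided linkage gives about 8 to 14%.

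A reader might go further in four ways that the documents do not support:

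- *Roxadustat will look better.* The direction is open: more prognosis-linked stopping on ESA biases the other way.
- *Unequal discontinuation alone causes bias.* With 36% vs 20% stopping for unrelated reasons, the HR is 1.00.
- *Every early stopper is censored.* Those admitted before stopping count as events.
- *The SAP contradicts the protocol.* The protocol sets no analysis window for this endpoint.

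This is a cheap improvement, not a threat to the trial's primary conclusions.

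**What to change.** 1. Confirm that dated admissions are available for the post-study period, from the hospitalization records or the SAE reports.
2. In SAP 6.1.3.6 and 7.4.3.6, add an analysis of occurrence and time to first hospitalization in all FAS subjects, to the earliest of actual or projected EOS, last contact or death, using the post-study hospitalization and SAE records. Take the projected EOS from the current protocol, because the SAP still describes follow-up to projected week 108.
3. State how death is handled (competing event or composite), and do not cut off admissions between the last Hb assessment and death.
4. Report this beside the EOT-censored analysis, and make no superiority statement unless the full-follow-up result supports it.

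Cost: SAP wording and modest programming, with no new collection if step 1 succeeds. The downside is some dilution of a true on-treatment effect. If dates prove unavailable, only occurrence can be compared over full follow-up, and the time-to-event result should be described as on-treatment, without a superiority statement.
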